8.3 DEFINITION OF DURATION OF TREATMENT AND DURATION OF EXPOSURE

The duration of treatment will be calculated using the following equation.

- Duration of treatment = date of last dose of study drug – date of first dose of study drug + 1

The duration of exposure will be calculated using the following equation.

- Duration of exposure = date of last dose of study drug – date of first dose of study drug + 1

If drug interruption occurs, then the drug interruption duration will be subtracted to calculate duration of exposure. For both duration, if the date of last dose of study drug is missing, the date of early discontinuation from study drug will be used instead. If the date of early discontinuation from study drug is also missing, the date of completion or discontinuation will be used instead.

8.4 DEFINITION OF CENSORING RULE FOR CONCOMITANT AD MEDICATIONS

For subjects who start a new AD medication (AChEIs and/or memantine) and were not on an AD medication at randomization, a flag will be set to “Yes” at the visit where the AD medication started and carry forward for all subsequent visits. For subjects who were on an AD medication at the time of randomization and a dose adjustment (increase/decrease/stop) to the AD medication is performed after randomization, a flag will be set to “Yes” at the visit of the dose adjustment and carry forward for all subsequent visits.

For the sensitivity analyses described in [Section 5.4.1](#), the separate analysis flag applying the visit window rule in [Section 7.2](#) after excluding the assessments flagged as “Yes” or after last dose date will be prepared in the datasets.

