- 2). To minimize the impact of intercurrent events (i.e., treatment discontinuation or change in concomitant AD medications), an MMRM analysis will be conducted on both FAS and PPS, by censoring the data after intercurrent events (i.e., treatment discontinuation, initiation of new AD medications [AChEI or memantine] and/or change in dose of current AD medications).
- 3). An ANCOVA model will be used after multiple imputation (MI) to evaluate the impact of missing data in both FAS and PPS. The following steps are described for multiple imputation.

Step 1 (imputing missing data): The dataset will be converted into monotone missing pattern by imputing intermediate missing data using MCMC approach first. The monotone data will then be imputed with monotone regression method. The imputation regression model will include treatment group, baseline CDR-SB and all available change from baseline in CDR-SB at post-baseline visits. There will be 1000 imputations, ie, 1000 imputed completed datasets, created with a predefined seed number (seed=2609). SAS PROC MI will be used to implement the imputation procedure. The sample SAS statement can be found in [Section 9](#).

Step 2 (performing ANCOVA using each imputed dataset): The ANCOVA model with factors of treatment group, randomization stratification variables (ie, region [7 levels], clinical disease staging [MCI due to AD, early stage of mild AD], and concurrent AD medication use at randomization (Visit 2) [yes, no]), *ApoE4* status, and baseline CDR-SB as a covariate will be applied to each imputed dataset. SAS PROC MIXED will be used for the ANCOVA. The sample SAS statement can be found in [Section 9](#).

Step 3 (combine results): Resulting treatment effect parameter estimators and standard errors from each of 1000 multiple imputed datasets from Step 2 will be combined using SAS PROC MIANALYZE to obtain the pooled treatment effect and variance parameter estimators according to Rubin's rules ([Rubin, 1987](#)). The sample SAS statement can be found in [Section 9](#).

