8.2 DEFINITION OF VISIT WINDOWS

The protocol specified visits/weeks and corresponding time windows used for visit-wise analyses are presented in terms of days relative to the first dose.

Different assessment may have different visit schedule. A general rule for determining a time window for each scheduled visit is to split the two consecutive scheduled visits in the middle point of the two consecutive visits. For example, the time window for visit X is from the middle point between visit (X-1) and X (exclusive) to the middle point between visit X and (X+1) (inclusive). Table 4 shows the case in primary endpoint, as example. The details for other efficacy/biomarker/safety endpoints will be specified in the programming specification.

Table 4. Visit Windows for Primary Endpoint

Analysis visit	Target visit day	Analysis visit window
Baseline	1	The value closest to and prior to (including on) the date of first dose
Week 13 Day 85	85	[43, 134]
Week 27 Day 183	183	[135, 228]
Week 40 Day 274	274	[229, 319]
Week 53 Day 365	365	[320, 410]
Week 66 Day 456	456	[411, 501]
Week 79 Day 547	547	[502, 592]
Week 92 Day 638	638	[593, 683]
Week 105 Day 729	729	[684, 753]

In addition, the following visits will be assigned separately (for efficacy/safety endpoints) if last dose date is known

- Last on treatment: the last post-baseline assessment on or before last dose date. [except EQ-5D/QOL-AD/Zarit's Burden Interview/C-SSRS]

- End of treatment: the earliest assessment on or after last dose date and before last dose date + 56 days (inclusive) [except C-SSRS]
- 12 week Follow-up visit: the closest assessment to last dose date + 84 days after last dose date, but after last dose date + 57 days (inclusive) [except EQ-5D/QOL-AD/Zarit's Burden Interview/C-SSRS]

For efficacy endpoints, the assessments at early discontinuation from study drug, follow-up visits, clinical assessments at 12 and 24 months, unscheduled visits will be assigned to analysis visit using the same visit window rule.

For safety endpoints, the assessments after last dose date + 8 days (inclusive) will not be included in the visit-wise analyses except specific visit described above (the analysis flag should not be "Y"). If last dose date is missing, the assessment at early discontinuation from study drug, follow-up visits and unscheduled visits on or after early discontinuation from study drug or follow-up visits will not be included in the visit-wise analyses.

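### The Section 8.4 censoring flag does not fully implement the intercurrent-event sensitivity analysis of Section 5.4.1: it misses AD drugs added by baseline users and, in two narrower cases, removes assessments that are not after any event

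*SAP*

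**What the plan says.** Section 5.4.1 of SAP v2.0 lists, as its second sensitivity analysis, an MMRM on the FAS and PPS carried out "by censoring the data after intercurrent events". The events are treatment discontinuation and "initiation of new AD medications [AChEI or memantine] and/or change in dose of current AD medications". No condition on AD-medication use at randomization is attached.

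Section 8.4 defines the flag in two branches:

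- New starts: "For subjects who start a new AD medication (AChEIs and/or memantine) and were not on an AD medication at randomization". The flag is set "at the visit where the AD medication started and carry forward for all subsequent visits".
- Baseline users: the flag is set at the visit where "a dose adjustment (increase/decrease/stop) to the AD medication is performed after randomization", and is likewise carried forward.

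Flagged assessments are then excluded, together with any that fall later than the last dose: the analysis flag is built after excluding assessments flagged Yes "or after last dose date will be prepared in the datasets".

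Section 5.4.2 repeats the intercurrent-event analysis for ADCOMS, time to worsening of CDR, time to conversion to dementia, ADAS-cog11, ADAS-cog14, MMSE, FAQ and the Word List. Section 8.4 cites only Section 5.4.1, but it is the only place where the SAP defines the censoring rule.

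**The concern.** A programmer who follows Section 8.4 to the letter produces a different analysis from the one in Section 5.4.1. The differences run in both directions.

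- **Too little censored.** A baseline user who adds a second AD drug has initiated a new AD medication under Section 5.4.1, yet no branch of Section 8.4 catches it. Concurrent AD medication use is a stratification factor, so baseline users are an expected part of the trial. Section 5.4.4 counts any post-randomization initiation as a change of AD treatment, so the SAP treats the same event in two ways.
- **Too much censored, at the event visit.** Section 5.4.1 removes data after the event. Section 8.4 starts the flag at the visit itself, so an assessment made at the visit where the drug was started or the dose changed is lost.
- **Too much censored, at the end of treatment.** Section 8.4 cuts on the last dose date, not on discontinuation. A subject who completed treatment but was assessed after the last dose loses the 24-month value with no intercurrent event.

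At stake is whether this analysis answers its stated question, which is the effect with the influence of discontinuation and AD-medication change minimized.

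**Working it through.** The SAP states no figure for this rule, so the check applies each text literally to hypothetical subjects on the Table 4 target days (85, 183, 274, 365, 456, 547, 638, 729).

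Rule from 5.4.1: keep assessments dated on or before the first event. Rule from 8.4: exclude the flagged visit and all later ones, and anything after the last dose date.

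| Case | 5.4.1 keeps | 8.4 keeps |
|---|---|---|
| A. Baseline AChEI user adds memantine at Day 365, first drug unchanged | Days 85–365 (4 visits) | Days 85–729 (8 visits) |
| B. Non-user starts at the Day 365 visit | Days 85–365 (4) | Days 85–274 (3) |
| C. Baseline user, dose change at the Day 365 visit | Days 85–365 (4) | Days 85–274 (3) |
| D. Non-user starts on Day 400, flag placed on the next visit | Days 85–365 (4) | Days 85–365 (4) |
| E. Completer, last dose Day 728, visit Day 729 | all 8 | 7, 24-month value lost |
| F. Completer, last dose and visit both Day 729 | all 8 | all 8 |
| G. Last dose Day 300 (early stop), visit Day 301 | drops Day 301 | drops Day 301 |

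Case A is a contradiction under any timing. Four post-event visits stay in, including the 24-month one. A switch would be caught, because stopping the baseline drug is named; a pure add-on is not.

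Cases B and C conflict only when the start or change happens at the visit. For a start between visits, Section 8.4 does not say which visit is meant. If it is the next one (D), the two sections agree.

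Cases E to G show that the last-dose cut departs from Section 5.4.1 only for completers assessed after the last dose.

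**Scale for cases B and C.** Excluding the event-visit value matters for bias only if that value influences prescribing, since the MMRM assumes missing at random. The SAP gives neither start rates nor a mechanism, so both were assumed:

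- random-slope CDR-SB, with 24-month placebo mean 1.46 and SD 2.05 (Section 4);
- arm difference 0.25 × 1.46 = 0.365;
- about 19–37% of subjects starting a drug, with odds rising with the decline seen at the visit;
- 200,000 subjects per arm.

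Two sets of such simulations shrank the arm difference by about 1–7% and 1–11%:

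- 0.01 × 0.365 = 0.004; 0.07 × 0.365 = 0.026; 0.11 × 0.365 = 0.040.
- Planned evaluable per arm: 950 × 0.70 = 665. Standard error of the difference: 2.05 × √(2/665) = 0.112.
- 0.026 / 0.112 = 0.23 and 0.040 / 0.112 = 0.36 standard errors. With fewer 24-month values after early termination the standard error is larger and these ratios smaller.

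No figure can be given for case A or case E, because the SAP reports neither how many baseline users add a drug nor how many completers are assessed after the last dose.

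**The case against.** The strongest reply is that Section 5.4.1 is clear, Section 5.4.2 repeats it, and Section 8.4 is a drafting slip that a sensible programmer would read through. The intent is indeed clear. But Section 8.4 is the derivation rule, its first branch expressly excludes baseline users, and its second names only an increase, decrease or stop. Reading an add-on as an adjustment of the whole regimen is possible but is not what the text says.

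Three stronger readings are tempting, and the documents do not support them.

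- **That cutting at the last dose with no allowance is itself wrong.** For subjects who discontinue, it is what Section 5.4.1 asks for, and it matches the last on-treatment visit in Section 8.2. The tolerances elsewhere govern other analyses, such as "For safety endpoints, the assessments after last dose date + 8 days (inclusive) will not be included in the visit-wise analyses" and the 28 days for amyloid PET in the same section. The early-discontinuation visit within 7 days of last dose appears only in the superseded v1.0 SAPs.
- **That the cut discards the last near-treatment value of nearly everyone stopped by the termination.** Nothing in the SAP dates those assessments relative to last dose, and Section 5.4.1 would itself drop values recorded after such subjects discontinued.
- **That excluding the event-visit value breaks the MAR assumption and seriously biases the result.** That follows only if prescribing responds to that visit's score, which is an assumption. The same simulations gave per-arm bias of roughly −0.08 to −0.28 points when the visit was dropped, but most of it cancels in the arm difference, which is what the analysis estimates.

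The completer case is also narrow. Section 5.2.6 uses 729 planned tablets and Table 4 targets Day 729, so on schedule the last dose and the visit coincide and the value is kept.

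**Conclusion.** Section 8.4 does not fully implement Section 5.4.1. The add-on omission holds on the text alone, with no assumption, and is the substantive error: the affected subjects keep all their post-event data. The event-visit exclusion holds only for starts or dose changes made at the visit. Its effect on the arm difference is small, at about 0.004 to 0.040 points under assumed start rates and an assumed prescribing mechanism. The completer loss holds only where the 24-month visit falls after the last dose.

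The primary analysis uses all observed data regardless of discontinuation or AD-medication change and is untouched. Section 5.4.1 does not rank its sensitivity analyses, so this one should not be called the main one. The correction should be made, but it does not threaten the primary conclusion.

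**What to change.** Rewrite Section 8.4 by date:

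1. The AD-medication event date is the earlier of (a) the first start of any AChEI or memantine not taken at randomization, whatever the baseline use, and (b) the first dose change or stop of an AD drug taken at randomization.
2. Exclude only assessments dated after the event date. This keeps same-day assessments and settles starts between visits.
3. Apply the last-dose cut only to subjects recorded as having discontinued study drug early, a status already captured for the Section 5.2.2 disposition tables.
4. State that the same flag serves the Section 5.4.2 sensitivity analyses, and correct the cross-reference to Section 7.2, since the visit windows are in Section 8.2 of SAP v2.0.

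The cost is a few lines of SAP text and one derivation, plus a convention for incomplete medication dates. The one compromise is that an assessment made later on the day of the first new tablet is treated as before the event.

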8.5 ALGORITHMS FOR EFFICACY PARAMETERS

This section describes the algorithms and missing data handling procedure to derive the totals scores for the efficacy parameters: CDR-SB, ADCOMS, ADAS-Cog₁₁, ADAS-Cog₁₄, MMSE, FAQ, ADAS-cog₁₄ Word list, and NPI-10.

CDR-SB: The CDR is a clinical global rating scale requiring the interviewing of both the subject and an informant who knows and has contact with the subject. The CDR is a clinician-directed assessment of both cognition and function, and is intended to capture the state and therefore the disease stage of the individual. The CDR assesses 6 domains of subject function; memory, orientation, judgment and problem solving, community affairs, home and hobbies, and personal care. Each of these items has a maximum possible score of 3 points and the total score is a sum of the item scores (sum of boxes) giving a total possible score of 0 to 18 with higher

scores indicating more impairment. If any domain has missing data then the CDR-SB will be missing.

ADCOMS: The derived ADCOMS is a weighted linear combination of 12 items from the three existing clinical scales: the ADAS-cog, the MMSE, and the CDR. These 12 items consist of the predictive variables A4, A7, A8, A11, M1, M7, C1, C2, C3, C4, C5 and C6, which have been selected from the clinical scales, the ADAS-cog, the MMSE, and the CDR. The names of these item and the corresponding scale names are described in Table 5.

Table 5: Predictive Variables for the Derived ADCOMS

Scale	Item ID	Item Name	PLS weight
ADAS-cog	A4	Delayed Word Recall	0.00847483
	A7	Orientation	0.017088
	A8	Word Recognition	0.003732761
	A11	Word Finding	0.016211
MMSE	M1	Orientation Time	0.041567
	M7	Drawing	0.038238
CDR	C1	Personal Care	0.054321
	C2	Community Affairs	0.1091
	C3	Home and Hobbies	0.089039
	C4	Judgment and Problem Solving	0.069493
	C5	Memory	0.058724
	C6	Orientation	0.078152

ADAS-cog = Alzheimer's Disease Assessment Scale, cognitive subscale, CDR = Clinical Dementia Rating, ID = identification, MMSE = Mini Mental State Examination, PLS = Partial Least Squares.

The derived composite score will be calculated from these predictive variables according to the formula:

$$\text{Derived composite Score} = A4 * 0.00847483 + A7 * 0.017088 + A8 * 0.003732761 + A11 * 0.016211 + (5-M1) * 0.041567 + (1-M7) * 0.038238 + C1 * 0.054321 + C2 * 0.1091 + C3 * 0.089039 + C4 * 0.069493 + C5 * 0.058724 + C6 * 0.078152.$$

The maximum derived composite score is achieved when each item is assigned the maximum score. This maximum composite score is 1.97. The range of this new composite score is therefore between 0 and 1.97.

If any subscale has missing data then the ADCOMS will be missing. ADAS-cog, MMSE and CDR assessed at same CRF visit are used to derive the composite score even they are assessed in separate date.

ADAS-cog₁₁ and ADAS-Cog₁₄: The ADAS-cog is the most widely used cognitive scale in AD clinical studies. The 14-item version (as shown in Table 6) is considered more sensitive for less

impaired populations such as MCI/Prodromal and mild AD subjects. ADAS-cog₁₁ consists of 11-item (Delayed Word Recall, Executive Function, and Number Cancellation are excluded). If any item score is missing then the Total Score is missing.

Table 6. ADAS-cog₁₄ Items and Algorithm for Derivation of Item Scores and Total Score

Item	Algorithm	Handling Missing Data	Score Range
1. Word Recall	Total the number of “No” responses for each trial. The subscore is the sum the scores from trials 1, 2, and 3, divided by 3.	If a trial is missing or partially done then trial score is missing. If a trial score is missing then the subscore is missing	0 to 10
2. Commands	Total the number of “No” responses from the 5 tasks	If any task is missing then the subscore is missing	0 to 5
3. Constructional Praxis	Count the number of “No” responses. The subscore is 0 = all 4 drawings correct 1 = 1 figure drawn incorrectly 2 = 2 figures drawn incorrectly 3 = 3 figures drawn incorrectly 4 = 4 figures drawn incorrectly 5 = no figures drawn, scribbles, parts of forms	If any task is missing then the subscore is missing	0 to 5
4. Delayed Word-Recall	Total the number of “No” responses.	If any response is missing then subscore is missing	0 to 10
5. Naming Objects / Fingers	Total the number of “No” responses. The subscore is 0 = 0-2 “no” responses 1 = 3-5 “no” responses 2 = 6-8 “no” responses 3 = 9-11 “no” responses 4 = 12-14 “no” responses 5 = 15-17 “no” responses	If any response is missing then subscore is missing	0 to 5
6. Ideational Praxis	Total the number of “No” responses.	If any response is missing then subscore is missing	0 to 5
7. Orientation	Total the number of “No” responses.	If any response is missing then subscore is missing	0 to 8
8. Word Recognition	For each trial, total the number of “1” responses. If the total is 12 or less, then the trial score = total. If the total is > 12 then trial score=12. The subscore is the sum the scores from trials 1, 2, and 3, divide by 3.	If a trial is missing or partially done then trial score is missing. If a trial score is missing then the subscore is missing	0 to 12
9. Remembering Test Instructions	The subscore is 0 = None, 1 = Very Mild, 2 = Mild, 3 = Moderate, 4 = Moderately Severe, 5 = Severe	If the response is missing then subscore is missing	0 to 5

10. Comprehension	The subscore is 0= None, 1= Very Mild, 2= Mild, 3= Moderate, 4= Moderately Severe, 5= Severe	If the response is missing then subscore is missing	0 to 5														
11. Word Finding Difficulty	The subscore is 0= None, 1= Very Mild, 2= Mild, 3= Moderate, 4= Moderately Severe, 5= Severe	If the response is missing then subscore is missing	0 to 5														
12. Spoken Language Ability	The subscore is 0= None, 1= Very Mild, 2= Mild, 3= Moderate, 4= Moderately Severe, 5= Severe	If the response is missing then subscore is missing	0 to 5														
13. Executive Function (Maze)	The subscore is based on the total number of seconds to complete the task and/or whenever the task was stopped due to 2 errors being made, as follows; 0 = 0-30 seconds 1 = 31-60 seconds 2 = 61 – 90 seconds 3 = 91 – 120 seconds 4 = 121-239 seconds 5 = 240 seconds or at least 2 errors	If the response is missing then the subscore is missing	0 to 5														
14. Number Cancellation	Adjusted Score = Total # correct targets crossed off minus Total # incorrect targets crossed off minus Total # times reminded of task. Then use Adjusted Score to determine the subscore as follows; 
 
 Adjusted Score	Subscore	
 
 ≥23	= 0	
 
 18-22	= 1	
 
 13-17	= 2	
 
 9-12	= 3	
 
 5-8	= 4	
 
 ≤4	= 5	
 
	Adjusted Score	Subscore	≥23	= 0	18-22	= 1	13-17	= 2	9-12	= 3	5-8	= 4	≤4	= 5	If any component of the adjusted score is missing then the subscore is missing	0 to 5
Adjusted Score	Subscore																
≥23	= 0																
18-22	= 1																
13-17	= 2																
9-12	= 3																
5-8	= 4																
≤4	= 5																
Total Score	Total Score = sum of the subscores above	If any subscore is missing then Total Score is missing	0 to 90														

MMSE: The MMSE is a cognitive instrument commonly used for screening purposes, for staging of disease severity and is often measured longitudinally in AD clinical studies to follow disease progression and treatment effects. MMSE is composed of 30 questions group into domains. For each of the MMSE domains add the correct responses. If a domain has missing data then the domain is missing. From the domains, one can compute the six items as show in Table 7. If any domain is missing then the item is missing. The MMSE Total Score (range 0 to 30) = sum of the six items. If any item score is missing then the Total Score is missing.

Table 7. MMSE Domains and Items

Domain	Score Range	Item	Score Range
1. Orientation to Time	0 to 5	1. Orientation to Time	0 to 5
2. Orientation to Place	0 to 5	2. Orientation to Place	0 to 5
3. Registration	0 to 3	3. Registration	0 to 3
4. Attention and Calculation ^a	0 to 5	4. Attention and Calculation	0 to 5
5. Recall	0 to 3	5. Recall	0 to 3
6. Naming	0 to 2	6. Language (Sum of Naming, Repetition, Comprehension, Reading, Writing, and Drawing)	0 to 9
7. Repetition	0 to 1		
8. Comprehension	0 to 3		
9. Reading	0 to 1		
10. Writing	0 to 1		
11. Drawing	0 to 1		
		Total Score	0 to 30

^a Spell WORD Forward, then Backward score is only use if Attention and Calculation score is not available

FAQ: The FAQ is composed of 10 activities. Each activity is rated as 0 = Normal, 1 = Has difficulty but does by self, 2 = Requires assistance, 3 = Dependent, 8 = Not Applicable. The Total Score is the sum of the 10 activity. If any activity is missing then the Total Score is missing. Activities marked as “Not Applicable”, are not use in the computation of the Total Score. However, in order to account for “Not Applicable” activity(s), the Total Score is weighted as follows;

Total Score = Total Score x 30 / (30 minus 3 times the number of activities marked “Not Applicable”)

ADAS-cog₁₄ Word list: The summation of “1. Word Recall” and “4. Delayed Word-Recall” from ADAS-cog₁₄ Items. The score range is 0 to 20. If any word recall score is missing then word list score is missing.

NPI-10: If NPI-12 is available instead of NPI-10, each sub scale and total score for NPI-10 will be derived from NPI-12 sub scales. If any sub scale is missing then total score (distress or domain score) is missing.

